**Participants:** Our plan is to complete the study on 120 men and women age 65-85yrs and 30 young adults who will only be studied at baseline. We are anticipating a target accrual of 179 subjects to account for an anticipated dropout rate of 20% in the intervention group.

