### Statistical analyses and Power:

For all variables in aim 1, the interest is in assessing if the change from baseline to post treatment differs by treatment arm. We will determine the influence of chronic inflammation on these outcomes in older adults grouped according to quartiles of a composite score including serum CRP and IL-6. The initial analysis will be stratified by inflammation composite score quartiles. Within a subgroup, the Wilcoxon rank sum test will be applied to test for difference in the change of outcome value pre and post treatment between the two treatment arms, placebo and n3-PUFAs. Additionally, generalized linear models will be used to assess the effect inflammation has on modifying the treatment effect by including interaction terms of a smoothing spline functional fit of the composite score with the treatment and time variables. The residuals from the regression will be used to assess distribution assumptions and variables will be transformed if required for appropriate statistical inference. All participants with at least a pre-treatment measurement will be included in the primary analysis utilizing the as-randomized study arm assignment for comparison. Efforts will be made to minimize missing data, but in the event of missing values, characteristics between those with observed values and with missing values will be compared. If no observed differences are identified, multiple imputation will be used with the primary analysis. Power calculations were performed for hypotheses related to mitochondrial physiology. We used the preliminary data where we measured effects of EPA on mitochondrial capacity. With mean  $JO_2 = 28.9 \text{ pmol/s/tissue}$  and  $\sigma = 4.891$ , a sample size of 15 per treatment group within an inflammation quartile gives 80% power ( $\alpha=0.05$ ) to detect a treatment difference in the difference from baseline to post treatment of  $5.18 \text{ pmol/s/tissue}$  (15% change). With 4 inflammation quartile groups, the total sample size will be 120, with

balanced randomization that gives 60 for each treatment arm in total. We believe that this expected difference is meaningful and realistic because our target population of older adults is known to exhibit reductions in mitochondrial capacity, and this degree of improvement would be physiologically important.

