The main outcome variables for specific aim 2 are: 1) mRNA expression of anabolic and metabolic signaling genes, 2) expression and activation (phosphorylation) of signaling proteins, and 3) whole-body protein turnover. Hypothesis 2a will be addressed using the pre-treatment measurements, including a baseline and 3 post-exercise time points for all individuals. For each outcome, linear random effects models with time point and the inflammation score interaction terms plus a random intercept for each individual will be estimated. The statistical analysis for hypothesis 2b will be similar to specific aim 1, wherein regression models will be estimated for each outcome variable and include an interaction term between assigned treatment arm and the inflammation score. Missing data and loss to follow-up will be handled as described above in aim 1. Power calculations were performed using the preliminary data in which protein synthesis was measured using the same exercise protocol proposed in this aim. We utilized a linear random intercept model with a baseline and 3 post intervention time point and assuming an exchangeable correlation matrix with pairwise correlation of 0.7 within an individual between time points. With  $\sigma = 0.025 \text{ %/hr}$ , a sample size of 30 per inflammation group gives 80% power ( $\alpha=0.05$ ) to detect a  $0.028 \text{ %/hr}$  slope change between inflammation groups in muscle protein synthesis in response to exercise. We believe that this minimal detectable difference is meaningful, realistic, and conservative.

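### Multiple imputation is promised only when participants with and without missing values look alike; the condition points the wrong way, and no method is given when they differ

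*Combined protocol and SAP*

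**What the plan says.** The missing-data rule is in section D, Statistical analyses and Power, under Aim 1. It has two steps. First, "characteristics between those with observed values and with missing values will be compared". Second, "If no observed differences are identified, multiple imputation will be used with the primary analysis". The text does not name the characteristics, the test, the threshold for a difference or the imputation model. It gives no method for the case where differences are found.

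The same paragraph sets the analysis population: "All participants with at least a pre-treatment measurement will be included in the primary analysis", by randomised arm. The first analysis listed is within inflammation quartiles, where "the Wilcoxon rank sum test will be applied to test for difference in the change of outcome value pre and post treatment" between the arms. An additional generalized linear model includes "interaction terms of a smoothing spline functional fit of the composite score with the treatment and time variables".

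For Aim 2 the plan says "Missing data and loss to follow-up will be handled as described above in aim 1". It also says "Hypothesis 2a will be addressed using the pre-treatment measurements", so six-month dropout affects hypothesis 2b and not 2a.

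The Participants paragraph of section D gives a "target accrual of 179 subjects to account for an anticipated dropout rate of 20% in the intervention group".

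**The concern.** The text says if, not only if, but no section available to read commits to imputation, or to any other method, once differences have been found. The commitment therefore covers the case where it does least. When the two groups look alike, the data are closest to missing completely at random, and a complete-case analysis is already roughly unbiased. When measured characteristics are related to missingness, they belong in an imputation model, and using them there can remove bias under missing at random. That is the case in which the plan promises nothing.

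Two things are at stake. The handling of an expected 20% dropout would be decided after the data have been seen. In addition, a participant with no post-treatment value has no change score. Unless values are imputed, the rank-sum comparison drops that participant, contrary to the commitment to include everyone with a pre-treatment measurement.

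**Working it through.** **How many values are at issue.** The inputs are in the Participants paragraph: accrual 179, 30 young adults studied at baseline only, 20% dropout.
- 120 / 0.8 = 150, and 150 + 30 = 180, against the stated 179. The 20% therefore applies to the randomised older group as a whole.
- Older participants: 179 − 30 = 149.
- Missing post-treatment values: 149 × 0.2 = 29.8, about 30. Completers: 149 × 0.8 = 119.2, about 119.
- Per quartile: 149 / 4 = about 37 participants, of whom 29.8 / 4 = about 7 are missing.

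**The plan's own power figure.** The inputs are in Statistical analyses and Power: 15 per arm within a quartile, σ = 4.891, difference 5.18, α = 0.05 (taken as two-sided).
- A two-sample t-test gives 79.9% power, against the stated 80%.
- So 4.891 acts as the SD of the change. If pre and post values have equal variance and correlation r, the raw SD is 4.891 / √(2(1 − r)): 4.13 at r = 0.3 and 6.31 at r = 0.7.

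**Size of a possible bias.** The following assumptions are not in the documents: 20% missing in each arm; dropout depends on baseline JO2 in one arm only, with a logistic slope of −0.6 or −1.2 per SD; r from 0.3 to 0.7. Those slopes put the baseline mean of the missing participants d = 0.57 or 0.99 SD below that of the observed ones. The completers' baseline mean is then 0.2 × d SD above that of the whole arm. Change falls by (1 − r) per unit of baseline. Hence

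bias (absolute value) = (1 − r) × 0.2 × d × raw SD.

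| r | d | raw SD | bias | share of 5.18 |
|---|---|---|---|---|
| 0.7 | 0.57 | 6.31 | 0.3 × 0.2 × 0.57 × 6.31 = 0.22 | 4% |
| 0.7 | 0.99 | 6.31 | 0.3 × 0.2 × 0.99 × 6.31 = 0.37 | 7% |
| 0.3 | 0.57 | 4.13 | 0.7 × 0.2 × 0.57 × 4.13 = 0.33 | 6% |
| 0.3 | 0.99 | 4.13 | 0.7 × 0.2 × 0.99 × 4.13 = 0.57 | 11% |

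Simulation with 400,000 participants per arm agrees, giving 0.21 to 0.57. If 4.891 is instead the raw SD, the range is 0.3 × 0.2 × 0.57 × 4.891 = 0.17 to 0.7 × 0.2 × 0.99 × 4.891 = 0.68, or 3% to 13%.

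Imputation by arm on baseline leaves the bias within about 0.02. That is expected, because the scenario is missing at random by construction. With the same dependence in both arms, complete-case bias is within about 0.03.

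**How often the unspecified branch is reached.** The plan gives no test, so assume baseline JO2 is compared at the 0.05 level in 149 participants (75 and 74 per arm). Under the one-arm scenario, simulation finds a significant difference in 27% to 28% of trials at slope −0.6 and in 68% to 69% at slope −1.2. Complete-case bias in those trials is about 0.21 to 0.55.

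**Reliability of the trigger.**
- With about 30 missing and 120 observed, a real 0.5 SD difference in a characteristic is detected 68% of the time.
- If 10 independent characteristics are each tested at 0.05 and data are missing completely at random, at least one difference appears with probability 1 − 0.95^10 = 40%. In those trials the plan would offer no method, although nothing is wrong.

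**The case against.** The strongest reply is that this is one missing branch with little effect on the test named. Imputation is valid when no differences are seen, and observed differences do not establish missing at random. Both points are true. They argue against making the choice depend on the comparison at all, which is the change proposed here.

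On consequence, the bias is small against the precision of one quartile. With 15 per arm the standard error is 4.891 × √(2/15) = 1.79, so 0.21 to 0.57 is 0.12 to 0.32 standard errors. In simulation of the one-arm scenario, the type I error of the within-quartile rank-sum test was 4.7% to 5.9%, against 4.8% to 5.1% with no dependence. This stands: that test's error rate barely moves. Power moves somewhat more. By the t-test, 80% becomes 70% to 77% or 83% to 87%, depending on the direction of the bias.

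The scenario is also a chosen one. Nothing in the documents suggests that dropout in a double-blind softgel trial depends on baseline JO2 in one arm only. This stands too.

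Finally, the additional model with treatment and time terms could keep baseline-only participants, and hypothesis 2b uses regression models, not rank-sum tests. However, the plan neither names such a model as its missing-data method nor says that it replaces the rank-sum test when differences are found.

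**Conclusion.** The concern holds and should be fixed. The defect is in the text and does not depend on the size of any bias: the plan commits to a method where it corrects least, and to none where measured characteristics predict missingness. With about 30 of 149 post-treatment values expected to be missing, the rule will be used.

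The consequence is modest and conditional. Under one-arm dependence on baseline, complete-case bias is 4% to 11% of the target difference (3% to 13% on the other reading of the SD). It is near zero if the dependence is the same in both arms. The documents do not show which will apply. Confidence is high on the fault in the rule; the bias figures are illustrations under the stated assumptions.

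**What to change.** Delete the condition. State one method that applies whatever the comparison shows, on all randomised older participants:
- either multiple imputation by arm, with the baseline outcome, the inflammation score and predictors of missingness in the model;
- or a likelihood-based repeated-measures model.

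If the within-quartile rank-sum test is kept, say how it is run and combined across imputed data sets. Use the comparison of characteristics only to choose auxiliary variables. Apply the same text to hypothesis 2b. A delta-adjusted sensitivity analysis for data missing not at random is a sensible addition, but the core fix does not depend on it.

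The cost is SAP wording and modest programming, somewhat more if rank-sum results are pooled over imputations for many outcomes. No new data are needed, and no stated sample size, power or alpha changes.

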## **Human Subjects**

### **1. Risks to the subjects**

**Human Subjects Involvement and Characteristics:** All protocols and all techniques to be used will be approved by the Mayo Clinic Institutional Review Board prior to initiation of any studies. Subject characteristics and exclusion criteria have been clearly specified above. All women of child bearing potential will have a negative pregnancy test within 24 hours of the study and will be advised to refrain from conception for at least two months after the study. No children will be studied. All subjects will be weight stable before enrolling in the study. Our plan is to complete the study on 135 participants.

**Sources of Materials:** Samples of blood, skeletal muscle, and adipose tissue obtained during the study will be used exclusively for research purposes. Data on body composition will be used only for research. No use will be made of pre-existing specimens.

***Muscle tissue:*** Two or three muscle biopsies (~300mg each) will be obtained during each inpatient study visit.

***Blood:*** 1 blood draw will occur during the screening visit (approximately 15ml). Each inpatient study will require 48 blood draws (approx 407mL blood). All specimens will be processed internally and stored in the study team laboratory.

***Adipose tissue:*** One subcutaneous abdominal fat biopsy (2-3g) will be obtained during each inpatient visit.

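### Aim 1's detectable difference of 5.18 is labelled a 15% change but is 17.9% of the only mean given, and its 80% power is an unstated t-test figure although the within-quartile test is Wilcoxon

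*Combined protocol and SAP*

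**What the plan says.** All of this is in the combined protocol and SAP, section Statistical analyses and Power, in the Aim 1 paragraph.

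- **Source of the inputs:** "We used the preliminary data where we measured effects of EPA on mitochondrial capacity". The inputs are a mean JO2 of 28.9 pmol/s/tissue and σ = 4.891. The plan does not say which arm or time point the mean belongs to, or whether σ describes a single measurement or a change.
- **Power claim:** "a sample size of 15 per treatment group within an inflammation quartile gives 80% power" at α = 0.05 (sidedness not stated), "to detect a treatment difference in the difference from baseline to post treatment of" 5.18 pmol/s/tissue.
- **Percentage and total:** the same sentence calls this difference a "15% change). With 4 inflammation quartile groups, the total sample size will be 120", with 60 per arm.
- **Planned test within a quartile:** "the Wilcoxon rank sum test will be applied to test for difference in the change of outcome value" before and after treatment, between the two arms.
- **Justification:** the paragraph ends by describing the difference as meaningful, realistic and physiologically important.

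No pre-post correlation is given for Aim 1. The Aim 2 paragraph does give one for its own calculation: "assuming an exchangeable correlation matrix with pairwise correlation of 0.7 within an individual between time points".

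**The concern.** The percentage does not agree with the two numbers printed beside it. The sample size is defended by the size of the effect, so a reader needs to know how large that effect is in relative terms. A reader who takes 28.9 as the base and 15% as the target would think the trial has 80% power for 4.335, a clearly smaller difference than 5.18.

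The 80% also carries no statement of the test behind it. If it comes from a t-test, it is not the power of the rank test that the plan will apply within each quartile.

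**Working it through.** **Inputs, all from the Aim 1 power paragraph:** mean 28.9; σ = 4.891; n = 15 per arm per quartile; difference 5.18; α = 0.05; stated power 80%; stated label 15%.

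**1. Reproduce the plan's figure.** Treat 4.891 as the SD of the change and use a two-sided two-sample t-test with 28 degrees of freedom.
- Standard error of the difference = 4.891 × √(2/15) = 1.786.
- Noncentrality = 5.18 / 1.786 = 2.90.
- Power = 79.9%, and the difference detectable with 80% power is 5.183.

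This matches the plan. Two alternatives do not: the normal approximation gives 82.7% (80% at 5.00), and a one-sided t-test gives 88.2%. The totals follow: 15 × 4 = 60 per arm, and 120 overall.

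**2. Check the percentage.**
- 5.18 / 28.9 = 17.9%.
- 15% of 28.9 = 4.335.
- Base that would make 5.18 equal to 15%: 5.18 / 0.15 = 34.5.
- One candidate is the raised value, 28.9 + 5.18 = 34.08: 5.18 / 34.08 = 15.2%. The documents do not say that this was the base.

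**3. Power if 15% of 28.9 was the target.** Same t-test, difference 4.335: noncentrality = 4.335 / 1.786 = 2.43, and power = 64.9%. Reaching 80% for that difference would take 21 per arm per quartile, or 21 × 2 × 4 = 168 in total.

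**4. Power of the planned Wilcoxon test at 5.18.** This was simulated with 15 per arm, change SD 4.891 and 200,000 trials per shape. The exact test rejects if U ≤ 64 or U ≥ 161 (true size 0.0453). The second column is the normal approximation without continuity correction. The shapes are assumptions.

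| Shape of the changes | Exact test | Normal approximation |
|---|---|---|
| Normal | about 76.5% | about 78% |
| Uniform (lighter tails) | 71.8% | 73.4% |
| Logistic | 80.4% | 81.6% |
| t with 5 df | 84.2% | 85.4% |
| Laplace | 85.8% | 86.8% |

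With normal changes the exact test reaches 80% at a difference of about 5.4.

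**5. What depends on the meaning of 4.891.** If it is the SD of a single measurement, equal at both times, then the SD of the change = 4.891 × √(2(1 − r)), where r is the pre-post correlation. At r = 0.5 this is again 4.891, so power is again 79.9%. For assumed values on either side, r = 0.3 gives a change SD of 5.787 and 65.8% power, and r = 0.7 gives 3.789 and 95.1%.

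**The case against.** The strongest reply is that the sample size does not depend on the percentage. The figures 15, 60 and 120 follow from 5.18 and 4.891, and that calculation is right. The label enters no formula, and the plan does not literally say that it is 15% of 28.9; another base may lie in preliminary data that are not shown. This stands as far as the arithmetic goes, and a reader should not infer that the sample size was miscalculated. It does not rescue the label. A percentage printed beside a single mean will be read against that mean, and no other base is named.

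A second reply is that sizing a rank test by a t-test is common practice and costs little. That is also largely right. The loss is about 2 to 4 points under normality, and it disappears or reverses with heavier tails. The Wilcoxon comparison is also described as the initial analysis, with regression models to follow. A reader might infer that the choice of test leaves Aim 1 underpowered; the figures do not support that. What remains is that the basis of the 80% is not stated.

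A reader might also infer a serious power deficit from the unlabelled SD. The documents do not show one. Reproducing the 80% shows that 4.891 was used as the SD of the change; it does not prove that it is one, and its place beside a mean level of JO2 leaves the other reading open. But low power requires a correlation below 0.5, which nothing in the documents supports. The 0.7 given for Aim 2 concerns another outcome and other time points, so it settles the matter in neither direction.

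Finally, the planned number completing the study differs between sections ("Our plan is to complete the study on 120 men and women age 65-85yrs and 30 young adults" against "Our plan is to complete the study on 135 participants"). That is a separate matter with no bearing on this calculation.

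**Conclusion.** The point holds as a mislabelled effect size and an unstated basis for the power. The difference that justifies the sample size is 17.9% of the only Aim 1 mean given, not 15%. The 80% is correct as a two-sided t-test figure (79.9%), provided that 4.891 is the SD of the change. For the named Wilcoxon test it is slightly optimistic under normality, at about 76 to 78%, and not optimistic for the heavier-tailed shapes examined.

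The size of the problem turns on which number the sponsor meant. If 5.18 is the target, the label is wrong or lacks its base, and the sample size stands. If 15% of 28.9 is the target, t-test power is about 65% rather than 80%. The documents do not settle which was meant, so neither a shortfall in patients nor its absence can be asserted from them.

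**What to change.** In the Aim 1 power paragraph:

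1. Restate the difference as 5.18 pmol/s/tissue, 17.9% of 28.9, or name the base that gives 15%.
2. If 15% of 28.9 (4.335) is the intended target, replace 80% power with about 65% at 15 per arm per quartile.
3. State that the 80% comes from a two-sided t-test, or give the power of the Wilcoxon test with its distributional assumption (about 77% under normality, 80% at about 5.4).
4. Confirm that 4.891 is the SD of the change. If it is the SD of a single measurement, give the pre-post correlation; the stated 80% corresponds to about 0.5.

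These are text changes. Their cost is that the stated power becomes slightly less favourable, or clearly less favourable if 15% of 28.9 is the target. Only if the sponsor held to that smaller target and to 80% power would more participants be needed (168 against 120 by the t-test).

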### **B. Background**

Many older adults suffer from derangements in skeletal muscle, including mitochondrial impairments, oxidative stress, insulin resistance, weakness, and fatigue. Exercise forestalls disease and disability in older adults, but many (15-20%) fail to demonstrate favorable adaptations even when interventions are painstakingly controlled (1-4). This so-called exercise resistance is particularly evident in older adults, who exhibit blunted anabolic responses to exercise and nutrition (5-7), which likely contributes to sarcopenia and attenuates adaptive responses to exercise. Early evidence shows that clearance of inflammatory cells in adipose tissue restores mitochondrial function and muscle mass in mice. In humans, we show that responsiveness to *acute* exercise is enhanced by omega-3 fatty acids (n3-PUFAs), putative suppressors of chronic inflammation, particularly in adipose tissue (8, 9). **Knowledge gap:** Despite evidence implicating inflammation in muscle dysfunction, a mechanistic link in the context of human aging is in early stages of investigation.

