At 0500h infusions of  $^{13}\text{C}_6$  phenylalanine at 1.0 mg/kg FFM/h and  $[^{15}\text{N}]$  tyrosine at 0.5 mg/kg FFM/h will be started after bolus of 1.0 mg/kg FFM  $[^{13}\text{C}_6]$  phenylalanine, 0.5 mg/kg FFM  $[^{15}\text{N}]$  tyrosine, and 0.5 mg/kg FFM  $[^{13}\text{C}_6]$  tyrosine. These are stable (non-radioactive) isotopes. Muscle biopsies from one *v. lateralis* will be obtained at 0830hrs for measuring baseline gene expression, protein expression, and mitochondrial function. Muscle biopsy samples will be collected under local anesthesia (2% lidocaine buffered with sodium bicarbonate) using a modified Bergstrom needle. A single abdominal subcutaneous fat biopsy will be performed at 0830 hrs under local anesthesia using sterile technique. Following the muscle and fat biopsies (~0900hrs), participants will perform a bout of unaccustomed unilateral knee extension exercise using only the leg without prior biopsies. Following a warm-up set, subjects will complete 8 sets of 10 repetitions at 70% of their 1-repetition maximum, determined at least 7 days prior. A second muscle biopsy will be obtained from the exercised leg 3 hours following exercise (~1230hrs).

Following the second biopsy (~1300hr), participants will consume a mixed liquid meal containing 15% protein, 55% carbohydrate, and 30% fat, approximately equal to 35% of resting energy expenditure determined from the REE on the outpatient study day. Arterialized blood samples will be taken from a heated hand vein for glucose, insulin, and c-peptide measurements at intervals over 5 h after the test meal, which will be consumed over 10 min. Blood samples will be collected at 30, 20, and 10 minutes before the meal and at 0, 5, 10, 15, 20, 30, 40, 50, 60, 75, 90, 120, 150, 180, 210, 240, 260, 280, and 300 minutes following the meal. We are collecting and washing red blood cells for storage for future testing. Resting energy expenditure and respiratory quotient will be measured by indirect calorimetry for 30 minutes under postabsorptive conditions (0700hrs) and postprandial (1430hrs). Participants will be given a meal from the hospital kitchen at approximately 1800hr before discharge.

The inpatient and 48 hour study day will be repeated following the 6 month intervention.

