### 48 hours post-exercise biopsy:

Participants will return to the CRTU for an outpatient study visit involving an additional muscle biopsy from the exercised leg 48 hours following the single bout of exercise.

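### The hypothesis 2a model allows only a random intercept, so it assumes equal variances and correlations at all time points; an unstructured covariance should be prespecified.

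*Combined protocol and SAP*

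**What the plan says.** Under Statistical analyses and Power, the Aim 2 text says that for each hypothesis 2a outcome a linear model with interactions between time and score "plus a random intercept for each individual will be estimated". The outcomes are mRNA expression, expression and phosphorylation of signalling proteins, and whole-body protein turnover. The data are the pre-treatment measurements, "including a baseline and 3 post-exercise time points for all individuals".

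The power statement makes the same assumption, "assuming an exchangeable correlation matrix with pairwise correlation of 0.7", with one standard deviation of 0.025 %/hr for all times.

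The statistical section mentions no random slope, heterogeneous or unstructured covariance, robust standard error or covariance sensitivity analysis. It does provide for residual checks and transformation, but in the Aim 1 text.

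In Section D, the baseline biopsy is taken from one thigh, followed by "unilateral knee extension exercise using only the leg without prior biopsies". Then "A second muscle biopsy will be obtained from the exercised leg 3 hours following exercise", and a later visit adds "an additional muscle biopsy from the exercised leg 48 hours following the single bout of exercise".

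**The concern.** A random intercept with constant residual variance is compound symmetry: one variance at all times and one correlation for all pairs. Three features of the study make that doubtful.

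- **Legs.** The 3 h and 48 h biopsies share a leg; the baseline biopsy comes from the other.
- **Spacing.** Baseline and 3 h fall on the same day, and 48 h is two days later.
- **Response.** People may differ in their response to exercise beyond what the inflammation score explains. The model lets the mean response vary with the score but gives no further person-specific response.

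Hypothesis 2a is tested through time-by-score contrasts. Compound symmetry gives all of them one pooled error, so if the true difference variances are unequal, the confidence intervals and p-values for individual times are wrong.

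**Working it through.** **Inputs from the documents:** σ = 0.025 %/hr, exchangeable ρ = 0.7, 30 per inflammation group, detectable difference 0.028 %/hr, 80% power, α = 0.05 (two-sided assumed). No standard deviation or correlation is given by time point, so every departure below is an assumption.

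**The plan's own figure.** The SD of a difference between two times is σ√{2(1 − ρ)} = 0.025 × √0.6 = 0.01936. Comparing 30 with 30 on one post-exercise time minus baseline, SE = 0.01936 × √(2/30) = 0.0050. The detectable difference is then (1.96 + 0.84) × 0.0050 = 0.0140, and power at 0.028 is 99.99%, which is not the stated result. The stated result is recovered as a difference in differences over four cells of 15: SE = 0.025 × √(4 × 2 × 0.3/15) = 0.0100, detectable difference 0.0280, power 79.96%. That reading is an inference and does not decide this point. What matters is that, under the plan's σ and ρ, every pairwise difference has the same variance and the random-intercept standard errors are correct.

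**What the model does otherwise.** Take three times: baseline (0), 3 h (1) and 48 h (2). Let D01, D02 and D12 be the variances of the pairwise within-person differences. With balanced data and free time means, the within-person mean square has expectation (D01 + D02 + D12)/6. The model gives every pairwise contrast twice that, which is the mean of the three D values. So

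model SE / true SE for time j versus baseline: r = √(mean D / D0j)

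type I error ≈ 2{1 − Φ(1.96 r)}

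**Worked example.** Let the 3 h SD be 1.5 times baseline, with all correlations 0.7. In units of baseline variance, D01 = D12 = 1 + 2.25 − 2 × 0.7 × 1.5 = 1.15, D02 = 0.60 and mean D = 0.967. Then r = √(0.967/1.15) = 0.92 at 3 h and √(0.967/0.60) = 1.27 at 48 h. The rejection rates are 7.2% and 1.3%.

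Correlations in the table are in the order 0–3 h / 0–48 h / 3 h–48 h.

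| Assumed covariance | D01, D02, D12 | r at 3 h (type I) | r at 48 h (type I) |
|---|---|---|---|
| Plan: equal SD, 0.7 throughout | 0.60, 0.60, 0.60 | 1.00 (5%) | 1.00 (5%) |
| 3 h SD ×1.5, 0.7 throughout | 1.15, 0.60, 1.15 | 0.92 (7.2%) | 1.27 (1.3%) |
| 3 h SD ×2, 0.7 throughout | 2.20, 0.60, 2.20 | 0.87 (8.8%) | 1.67 (0.1%) |
| Equal SD, 0.7/0.5/0.5 | 0.60, 1.00, 1.00 | 1.20 (1.9%) | 0.93 (6.8%) |
| Equal SD, 0.8/0.5/0.5 | 0.40, 1.00, 1.00 | 1.41 (0.6%) | 0.89 (8.0%) |
| Equal SD, same-leg pair higher, 0.6/0.6/0.8 | 0.80, 0.80, 0.40 | 0.91 (about 7%) | 0.91 (about 7%) |
| Both post-exercise SDs ×1.5, 0.7 throughout | 1.15, 1.15, 1.35 | 1.03 (4.4%) | 1.03 (4.4%) |

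Simulation with two groups of 30 and 20,000 replicates agreed with the ratios to within about 0.01. The most extreme case tried (SDs 1/2/1.2, correlations 0.5/0.8/0.5, 120 people, continuous score) rejected 9.4% at 3 h and 0.01% at 48 h. With contrast-specific variances, which is what an unstructured covariance supplies, rejection stayed at about 4.5% to 5.5% in the settings simulated with 120 people.

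**A person-specific response shared by both post-exercise times.** Let it have variance t, with residual variance e. Then D01 = D02 = t + 2e and D12 = 2e. With t = e = 0.3 these are 0.9, 0.9 and 0.6, with mean 0.8, so r = √(0.8/0.9) = 0.94 and the type I error is about 6.5% at both times.

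**The case against.** The strongest objection is that nothing in the documents shows compound symmetry to be false. They give no variance or correlation by time, and under the stated ρ = 0.7 the test holds 5%. That stands, and it makes the size of the problem conditional.

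A reader might go further and infer that standard errors will be too small at 3 h and too large at 48 h, giving false positives at one and lost power at the other. The documents do not support this. It requires D01 > mean D > D02, that is, a 3 h change more variable than the 48 h change. Correlation that falls by 48 h reverses the pattern, and a higher same-leg correlation or a shared person-specific response makes both standard errors too small. The Background remark that "many (15-20%) fail to demonstrate favorable adaptations even when interventions are painstakingly controlled" does not help: it concerns adaptation to exercise interventions, not the variance of acute outcomes at particular hours.

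Three further objections stand in part.

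- The plan names no 3 h or 48 h contrast as its main test, and its power statement speaks of a slope. A joint time-by-score test is less affected: in simulations with 120 people it rejected 5.5% to 7.2%.
- The Aim 1 residual check and transformation, if carried over to Aim 2, could reduce unequal variances. They would not repair unequal correlations.
- Whole-body turnover is tracer-based and need not follow the biopsy times, so the leg argument does not reach it. It is still given the same covariance structure without justification.

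**Conclusion.** The point holds in conditional form. The hypothesis 2a model imposes compound symmetry without justification on outcomes whose sampling design makes it doubtful. If the pairwise difference variances are unequal, standard errors for time-specific time-by-score contrasts are wrong, and the sign of the error at each time depends on a covariance that the documents do not give. The range of about 0% to 9% for a single nominal 5% contrast rests on assumed covariances, three time points and complete data. No direction at 3 h or 48 h should be claimed.

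The calculation uses three times because Section D describes a baseline and two post-exercise biopsies, whereas the statistical text models three post-exercise times. The Human Subjects section leaves the count open too, allowing two or three biopsies per inpatient visit. These places must be reconciled. With four times the mechanism is the same, but the figures would change.

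**What to change.** In the hypothesis 2a model, treat time as categorical and replace the random intercept with an unstructured within-person covariance: three variances and three covariances for three times (six parameters), or four and six for four times (ten). Add a small-sample degrees-of-freedom correction. If the model does not converge, fall back to the random intercept with robust standard errors. State this rule in advance for all outcomes, so that the covariance is not chosen outcome by outcome after the data are seen. Reconcile the number of time points first, and match the structure to each outcome's actual sampling times.

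This needs no extra participants, visits or samples, and six or ten parameters are readily estimated from about 120 people. If compound symmetry is in fact true, the loss of efficiency is negligible. With three times, error degrees of freedom for a contrast fall from about 2 × 118 = 236 to about 118, moving the two-sided 5% critical value from 1.970 to 1.980, or about 0.5%.
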